Exhaled breath collection and analysis: Subjects will be asked to fast for a minimum of 1-2 hours prior to breath sampling, with an ideal fast of 4 hours or longer. Where possible sampling will be performed on a day when subjects are fasting as part of their routine care (e.g. prior to CT-PET or endoscopy). Before breath sampling, subjects will also be asked to rinse their mouth with water. Following a period of relaxed tidal breathing subjects will be asked to exhale directly in to double thickness Nalophan® bags (Scentroid, Canada).

Breath samples will be immediately (within 30-120 mins of collection, target: 30 minutes) transferred from Nalophan sample bags to thermal desorption (TD) tubes (Markes International, Llantrisant, UK) pre-packed with 200 mg of Tenax and 100 mg of Carbograph 5. 500ml aliquots of breath will be transferred to four TD tubes via a handheld precision pump (Easy-VOC, Markes International, Llantrisant, UK). TD tubes will be securely capped and stored at -80°C prior to being transferred to Imperial College London for analysis.

TD tubes containing exhaled VOCs will be analyzed by Gas Chromatography Mass Spectrometry (GC-MS). For thermal desorption GC-MS analysis, adsorbent tubes will be loaded into a sample tray (TD-100, Markes International). The tube will be dry-purged for 1 minute to remove excess moisture and air. VOCs will be desorbed from the tube by a specific combination of heat and gas flow and will be refocused on the cold-trap. The cold-trap is then rapidly heated to 290°C with carrier gas flow so that VOCs are transferred to the GC column in a narrow band. For separation, the GC column will be ramped. The mass spectrometer will run in electron impact ionisation mode, scanning mass ions 20-250 m/z. An initial solvent delay will minimize interference from water. Chromatographic data will be analyzed using the Mass Hunter package (Agilent Technologies) in combination with the NIST mass spectral library (2014, Maryland, USA) for compound identification and semi-quantification.

Urine sampling and analysis: Patients will be asked to provide a clean catch urine sample (approximately 10ml) into a sterile sample container. Urine samples will be aliquoted and stored at -80°C prior to being transferred on dry ice to Imperial College London for analysis.

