VOCs within the headspace gas above urine samples sealed in air-tight vials will be analyzed by GC-MS. Urine samples (2ml) will be diluted in 6ml deionized pure water, acidified using HCl to pH 2.0. Urine osmolality (OsmoPRO®, Advanced Instruments, Norwoor, UK) will be analyzed for the purpose of subsequent standardization. Samples will be placed in air tight headspace vials into which a HiSorb probe (Markes International, Llantrisant, UK) will be inserted. Headspace vials including the HiSorb probe will be heated and agitated at 60°C for 30 minutes. Headspace VOCs extracted

onto HiSorb probes will be analyzed using an Agilent 7890B GC with 5977 MSD (Agilent Technologies, Cheshire, UK) coupled to a Markes TD-100 device.

Saliva sampling and analysis: Subjects will be asked to fast for a minimum of 1-2 hours (Target: 4 hours) prior to saliva sampling. Where possible saliva sampling will be performed on a day when subjects are fasting as part of their routine care (e.g. prior to CT-PET or endoscopy). Saliva samples (1-3ml) will be collected by asking subjects to spit into a sample pot. Saliva samples will be aliquoted and stored at -80°C prior to being transferred on dry ice to Imperial College London for analysis.

Bacterial RNA will be extracted from saliva samples and analyzed by 16S rRNA gene amplicon sequencing to identify the species composition. Bacterial community types derived from tissues biopsies will be identified by cluster analysis of compositional data from 16S rRNA sequencing. Bacterial interaction networks will be constructed to identify any keystone species.

Patient demographics and metadata: essential accompanying patient demographics and metadata will include: age; sex; comorbidities; height; weight; tumor histology and stage; details of (neo)adjuvant therapy; details of surgery; duration of pre-test fasting, and; radiological parameters (tumor dimensions, nodal burden and PET-standardized uptake value). Where possible, data will be obtained via the IRB approved institutional database (IRB18-076).

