Statistical analysis: Both univariate and multivariate data analysis techniques will be applied to identify breath and urinary VOCs with the best discriminating ability and to develop a multivariate discriminant analysis model. Appropriate univariate statistical techniques will be used to compare intra- and inter- individual variability in exhaled VOCs in response to therapeutic intervention. Associations between predominant bacterial species and VOCs will be determined through a univariate and multivariate data analysis techniques.

Using the data collected, several machine learning algorithms will be adapted, trained and evaluated for the purpose of diagnostic inference based on the breath sample chemical analysis. We will start with an exploratory analysis of the VOC concentration data, including Principal Component Analysis (PCA) and Multi-dimensional Scaling (MDS), to reduce the feature space and develop intuitions about the data. Next, Machine Learning Algorithms (MLA) such as Support Vector Machines (SVM) and k-Nearest Neighbors (kNN) will be trained and validated to reliably separate cancer from non-cancer cases. An Information Theory based MLA will also be developed. Cross-validation algorithms such as k -fold training will be used to rigorously assess the reliability of the learning algorithms. Models will then be compared through suitable accuracy scores and ROC curves will be produced to aid the selection of appropriate clinical diagnostic measure, which balances specificity against sensitivity.

Sample storage

Breath, urine and saliva samples will be stored in a -80°C freezer within the Benaroya Research Institute. Samples will be deidentified and only labeled using a unique study identifier composed of the patient's study ID and the date the sample was collected.

Data storage

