This study will involve the handling, storage and transportation of sensitive patient data including: consent forms; demographic data; meta-data; questionnaire responses, and results of physiological and biochemical analysis.

With the exception of consent forms, all data will be stored in a pseudonymized form using patients' unique study ID. Electronic data will be stored within password protected institutional computers. Paper records and clinical samples will be stored within appropriate institutional facilities protected by mechanical and/or electronic security controls. Only the principal investigator will have access to the code linking patient identities to pseudonymized data and the link will not be broken.

Patient demographics and meta-data, will be collected either in paper or electronic (Microsoft Office Excel) form. Where data are collected in paper form they will be subsequently transcribed to the electronic database.

Breath, urine and saliva samples will be labelled using a unique study identifier composed of patient's study ID and date sample was collected. It will not contain PHI.

All samples transferred to Imperial College London for the purpose of analysis will be done so in a linked anonymized form, such that patients cannot be identified by outside parties. The link will never be provided in the future.

Once data analysis is complete, the data obtained in this study will be added to the IRB approved institutional database (IRB18-076). All research specific paper records associated with this protocol will be securely archived and stored for a minimum of 10 years after the study closes. The data will be stored long-term under IRB18-076 and any archival will follow as indicated in that protocol.

Risk of physical harm

It is considered that the risk of physical harm associated with this study is negligible. All interventions are non-invasive.

Identifying and reporting adverse events

Reporting Procedures

All adverse events (serious or non-serious) that are directly related to study activities will be reported. Adverse events (serious or non-serious) that occur as a result of patient's disease process or routine care, and any AEs that are not directly related to study procedures, will not be reported.

Depending on the nature of the event the reporting procedures below should be followed. Any questions concerning adverse event reporting should be directed to the local Principal Investigator.

Non serious adverse events

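### The study ID plus collection date label identifies a patient-day, not a container, and lets the laboratory put a patient's samples in time order

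*Protocol*

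**What the plan says.** The label is fixed in two places in the protocol. Under Sample storage, samples are "only labeled using a unique study identifier composed of the patient's study ID and the date the sample was collected". Under Risk of breach of confidentiality the rule is given again, without the word only: "Breath, urine and saliva samples will be labelled using a unique study identifier composed of patient's study ID and date sample was collected".

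The collection sections show what has to be labeled. Under Exhaled breath collection and analysis, "500ml aliquots of breath will be transferred to four TD tubes via a handheld precision pump". For the fluids, "Urine samples will be aliquoted and stored" and "Saliva samples will be aliquoted and stored"; the number of aliquots and the type of container are not given. All three sample types are requested at each of four time points.

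Breath tubes are "stored at -80°C prior to being transferred to Imperial College London for analysis". Samples reach that laboratory in linked anonymized form, and no step that removes or recodes the date is described. The primary aim is change in exhaled VOCs during treatment, and the Critical knowledge gap paragraph anticipates that target VOCs fall after chemoradiotherapy or resection.

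**The concern.** Two things follow from the stated label.

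First, an identifier called unique is shared by every container that a patient provides on one day. A result from one of four breath replicates cannot be tied by its label to a particular tube, so a failed or repeated run cannot be followed. Urine and saliva aliquots from one visit carry the same label and are both kept at -80°C; if their containers look alike, the label does not separate them. The protocol has samples destroyed during or after analysis, which limits later checking.

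Second, the label carries the date to the people who produce the measurements. The earliest date under a study ID is normally the pre-treatment sample. Where the direction of change is stated in advance and the readout is compound identification and semi-quantification from chromatograms, knowledge of time order gives expectation a way into the primary comparison.

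**Working it through.** The protocol gives no error rate, power or drift figure, and its sample size of 50 is pragmatic, so there is no stated figure to reproduce. The check is a count, followed by a comparison of sections.

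**Inputs**
- Patients: 50 (Sample size).
- Time points: 4 (Study time points).
- TD tubes per breath collection: 4 (Exhaled breath collection and analysis).
- Urine and saliva aliquots per visit: not stated; assumed 1 to 3 of each.
- Assumed: all samples of a time point are taken on one date, and all patients attend all time points.

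**Count**
- Distinct labels = patients × time points = 50 × 4 = 200.
- Containers per label = 4 + urine aliquots + saliva aliquots.

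| Aliquots of each fluid (assumed) | Containers per label | Containers in total |
|---|---|---|
| 1 | 4 + 1 + 1 = 6 | 6 × 200 = 1,200 |
| 2 | 4 + 2 + 2 = 8 | 8 × 200 = 1,600 |
| 3 | 4 + 3 + 3 = 10 | 10 × 200 = 2,000 |

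Of these, 4 × 200 = 800 are TD tubes. If every patient also gave the optional second baseline breath sample on another date, there would be 50 × 5 = 250 labels and 250 × 4 = 1,000 TD tubes. Missed visits lower the totals but not the number of containers per label. If the fluids were taken on a different day from the breath, the four TD tubes of one collection would still share a label.

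**What the label reveals**
- It carries study ID and date, with no field for time point, sample type or tube number.
- Sorting one patient's labels by date gives the order of the samples. The first is pre-treatment if that sample was taken.
- The order is not a perfect guide to stage. Baseline may span two dates, a time point may be missed without counting as a deviation, and subjects who turn out not to have tri-modality treatment are sampled too.
- Nothing in the protocol masks laboratory staff to the order.

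**The case against.** The strongest reply is that both label sentences are privacy wording. One is about deidentification; the other sits under confidentiality and goes on to say that the label holds no protected health information. Read that way, neither bars a tube or sample-type suffix. This is fair as to intent, but the Sample storage text still names two fields, restricts the label to them and calls the result unique. Someone following it would produce the shared labels counted above.

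It can also be said that little harm follows from a tube mix-up. This largely stands. The four TD tubes hold aliquots of one breath collection, so swapping them changes neither patient, date nor stage. TD tubes are physically unlike fluid containers, and other patients and days have other labels. What remains is replicate-level traceability and a possible mix-up of same-day urine and saliva aliquots.

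On masking, peaks are processed with software and a spectral library, and no subjective review is described. The protocol does not exclude judgment at that step either, so masking is a precaution against a plausible bias, not the cure of a demonstrated one.

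A reader might go further and infer that run order will follow treatment stage, so that instrument drift cannot be separated from treatment change. The protocol does not support this. A date on a label neither sets nor prevents a run order, and the protocol nowhere says that samples are run by date or stage. Run order may be covered in a laboratory procedure or an analysis plan that is not shown. Even under date-order running, patients enter over about a year, so samples of different stages fall on similar dates and confounding would be only partial.

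The same reader might attach a false-positive rate. With a constant shift of b SDs of the paired difference, fully aligned with stage, a two-sided 5% test at n = 50 rejects with probability Φ(b√50 − 1.96) + Φ(−b√50 − 1.96). This is 29.3% for b = 0.2 and 80.7% for b = 0.4 (28.4% and 79.2% with the paired t-test). Both the shift and its full alignment are assumptions. The figures illustrate a worst case and do not measure this protocol.

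**Conclusion.** The point holds in a limited form. The identifier called unique identifies a patient-day. At least 6 containers share each label, or about 1,200 containers on 200 labels, assuming one aliquot of each fluid, same-day collection and full attendance. The consequences are lost replicate traceability and a possible mix-up of same-day urine and saliva aliquots.

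The more important consequence for the analysis is that the mandated date lets laboratory staff order a patient's samples, and usually recognize the pre-treatment one, while a post-treatment fall is expected. The protocol gives no basis for sizing the bias that this could cause, and none is claimed here. The change is worth making because it corrects a stated rule at almost no cost and protects the primary longitudinal comparison.

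**What to change.** In Sample storage and in Risk of breach of confidentiality, replace the label with a random code for each container. The code should carry no date but should still show sample type and tube or aliquot number. The laboratory needs the sample type, because urine is acidified and extracted for headspace analysis while saliva goes to RNA extraction and sequencing.

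Keep the key from code to study ID, date and time point at the recruiting site until peak data are locked, and state that laboratory staff are masked to time point until then. Releasing that key afterwards does not disclose patient identity, so the commitment never to share the identity link is unaffected.

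Add a sentence that samples are run in random order within each batch, with time points mixed across batches, and that batch and storage duration are recorded for the analysis. Staggered entry should allow much of this mixing without long holding. Holding all of one patient's tubes for a single batch is not advised as a general rule: the last time point falls six months to one year after surgery, so this would itself tie storage time to stage.

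The cost is a label list, a run sheet and possibly longer freezer storage of some tubes. No extra samples or visits are needed.
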